3.2 STUDY OUTCOME MEASURES

3.2.1 Primary Outcome Measure

Comparison of the change in mean daily Wong-Baker FACES Pain Rating Scale (limited to abdominal pain) during weeks 1-2 (initial observation phase) and the double-blind phase (week 3-6) recorded in the daily diary in the Enterosgel® versus the placebo arm.

3.2.2 Secondary Outcome Measures

3.2.2.1 Double-blind and Open-label treatment phase

The secondary outcome measures in the Enterosgel® versus the placebo arm during the double-blind and open-label treatment phase are listed in **Table 1**.

Table 1. Secondary outcome measures for the double-blind and open-label treatment phase

Outcome Measure	Time points and method of assessment	Definition
1. Abdominal pain score	Daily diary	Mean daily Wong-Baker FACES Pain Rating Scale
2. Frequency of abdominal pain	Daily diary	Proportion of days with any abdominal pain
3. Days missed nursery/school	Daily diary	Proportion of days missed nursery/school
4. Change in the Stomach Pain and Hurt total score	Baseline, weeks 6 and 10 (PedsQL 3.0 GIS module; comprised of 6 items)	Parent/carer proxy-report for 3-4-year-olds and child self-report from 5-18 years; by parent/carer proxy-report for 3-18-year-olds)
5. Change in individual components of the PedsQL 3.0 GIS module	Baseline, week 6, 10 (PedsQL 3.0 GIS module)	Parent/carer proxy-report for 3-4-year-olds and child self-report from 5-18 years; by parent/carer proxy-report for 3-18 years old. Individual components of the PedsQL 3.0 GIS module: stomach discomfort when eating (5 items), food and drink limits (6), trouble swallowing (3), heartburn and reflux (4), nausea and vomiting (4), gas and bloating (7), constipation (14), blood in bowel movement (2), diarrhoea (7), worry about bowel movements (5), medicines (4), communication (5).
6. Change in total PedsQL 3.0 GIS module score	Baseline, week 6,10 (PedsQL 3.0 GIS module)	Parent/carer proxy-report for 3-4-year-olds and child self-report from 5-18 years; by parent/carer proxy-report for 3-18 years old.
7. Change in health-related quality of life KIDSCREEN- 27 questionnaire	Baseline, week 6, 10 (Health-related quality of life KIDSCREEN-27)	Total Health-related quality of life KIDSCREEN- 27 score (parent reported 3-7 years, child self- report 8-18 years)
8. Change in health-related quality of life KIDSCREEN-27 questionnaire "General Mood and Feelings about Yourself" sub- score	Baseline, week 6, 10 (Health-related quality of life KIDSCREEN-27)	Health-related quality of life KIDSCREEN-27 sub-score for "General Mood and Feelings about Yourself" (7 questions; parent reported 3-7 years, child self-report 8-18 years)
9. Acceptability of the study interventions	Daily (diary)	Compliance with taking study intervention each day*

10. Adequate relief	Questionnaire	Opinion of the 1) child and 2) parent/carer whether there has been adequate relief of abdominal pain during the previous 7 days (recorded at end of double-blind and open-label phases)
11. Use of common analgesics for abdominal pain	Questionnaire	 Use of common analgesics (e.g. paracetamol; ibuprofen) for abdominal pain in the last week of the initial observation period (week 2), double blind phase (week 6) and open label phase (week 10)
12. Adverse Events	When reported	 Percentage of patients reporting SAEs and AEs possibly related to treatment Total number of SAEs and AEs reported

*Patients who develop constipation will be advised to stop treatment for a few days as per study treatment instructions. The diary will capture this information which will not be considered as non-compliance.

Data regarding the PedsQL 3.0 GIS module and KIDSCREEN-27 questionnaire will be collected as an online version (for use on mobile devices, laptops and computers). The PedsQL 3.0 GIS module will be a proxy-report completed by the parent/carer for 3-4-year-olds and child self-report from 5-18 years. The KIDSCREEN-27 will be a proxy-report completed by the parent/carer for 3-7 year-olds and child self-report from 8-18 years. The "General Mood and Feelings about Yourself" sub-score (based on 7 questions) will be analysed to assess effects of the intervention on anxiety/depression in addition to the "worry about bowel movements" (5 questions) in the PedsQL 3.0 GIS module. The content of the diary is supplied in Error! Reference source not found..

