2. AIMS AND OBJECTIVES

2.1 AIMS

The aims of this study are:

- 1. To determine the efficacy of Enterosgel® treatment for 4 weeks in improving FAPD symptoms in children with Functional dyspepsia [H2a], IBS [H2b]; Abdominal migraine [H2c] or Functional abdominal pain not otherwise specified [H2d])
- 2. To determine the safety and tolerability of Enterosgel® for the treatment of FAPDs
- 3. Document the effects of treatment up to 8 weeks on symptoms
- 4. To determine the efficacy in sub-group analysis of children with specific FAPDs.
- 5. To obtain data to power a larger follow-on study to determine the clinical and cost effectiveness of Enterosgel® for the treatment of FAPDs in children.

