2.2.2 Secondary objectives

The secondary objectives for the **double-blind treatment phase** (weeks 3-6) are:

- 1. To determine the efficacy of Enterosgel® compared with a parallel placebo group in terms of:
 - abdominal pain as recorded in the daily diary
 - change in stomach pain and other gastrointestinal symptoms
- 2. To determine effects of treatment on health-related quality of life
- 3. To evaluate safety of Enterosgel® through reported adverse events potentially related to treatment

The secondary objectives for the open-label treatment phase (weeks 7-10) are:

- 4. In patients who had received placebo as blinded treatment, to compare the study outcome measures (same as for double-blind phase above) over the open-label Enterosgel® treatment period to the preceding placebo treatment period.
- 5. In patients who had received Enterosgel® as the blinded treatment, to test whether the treatment benefits (in terms of study outcome measures; same as for double-blind phase above) can be effectively maintained with Enterosgel®.
- 6. To evaluate safety of Enterosgel® through reported adverse events potentially related to treatment.

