7.1.1 Adverse Event (AE)

Any untoward medical occurrence, unintended disease or injury or any untoward clinical signs (including an abnormal laboratory finding) in subjects, users or other persons whether or not related to the investigational medical device.

NOTE 1: This includes events related to the investigational device or the comparator.

NOTE 2: This includes events related to the procedures involved (any procedure in the clinical investigation plan).

NOTE 3: For users or other persons this is restricted to events related to the investigational medical device.

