7.2 RECORDING AND REPORTING OF ADVERSE EVENTS

7.2.1 Investigational procedures and treatment

AEs will be collected throughout the study from screening appointment until week 10. If an AE is reported by the patient, the relationship of the event to the study treatment or procedures should be assessed by the local PI, or a delegated sub-PI or nurse. The following information will be recorded for all AEs:

- Medical term of the AE (SNOMED CT terminology)
- Start date and date of resolution
- Seriousness
- Severity
- Study treatment action
- Outcome
- Relationship with the study treatment
- Expectedness

SADEs, SAEs, and USADEs should always be recorded in the eCRF and reported to the Sponsor using the Sponsor's SAE reporting form. Any SAEs that occur during the screening period that resulted from the administration of any study procedures and are unexpected, should also be reported. The form should be emailed to the Trial Manager ([contact]) within 24 hours of the site team becoming aware of the event. If the site does not receive an acknowledgement of the receipt of the report within 24 hours, they should immediately contact the Trial Manager by telephone.

The Sponsor should immediately inform the CI of any reported SAEs. The CI should review the SAE to confirm causality and expectedness.

The Sponsor should also report all serious adverse events, whether initially considered to be device related to the MHRA (Any SAEs which indicate an imminent risk of death, serious injury or serious illness, and which requires prompt remedial action for other subjects, shall be reported within two calendar days of awareness, any other SAEs shall be reported within seven calendar days). The REC should be notified of any related and unexpected SAEs within 15 days. Reports of related and unexpected SAEs in double-blind trials should be unblinded. Investigators should only receive information on the code-break if it is necessary for the safety of the patient.

SAEs should be followed-up until resolution or a final outcome. All follow-up information should be emailed to the Sponsor as soon as it becomes available. The SAE form and any email correspondence related to the SAE should be filed in the investigator site file and in the electronic Trial Master File.

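### The only child-level adverse event measure, and both safety objectives, are filtered by judged relatedness; all-cause events are counted only as a total

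*Protocol*

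**What the plan says.** - **Aim (2.1).** Unrestricted: "To determine the safety and tolerability of Enterosgel® for the treatment of FAPDs".
- **Safety objectives 3 and 6 (2.2.2, repeated in the Trial Summary).** Safety is evaluated "through reported adverse events potentially related to treatment", in the double-blind and the open-label phase respectively.
- **Outcome 12 (Table 1, 3.2.2.1).** Two measures: "Percentage of patients reporting SAEs and AEs possibly related to treatment" and "Total number of SAEs and AEs reported". The table applies to both phases.
- **Definition of an AE (7.1.1).** Unrestricted: "whether or not related to the investigational medical device".
- **Who judges relatedness (7.2.1).** It "should be assessed by the local PI, or a delegated sub-PI or nurse". The Chief Investigator then reviews causality for SAEs only.
- **What is captured (7.2.1).** "The following information will be recorded for all AEs", followed by a list that includes term, seriousness, severity and relationship.
- **Safety population (8.3.3).** All randomised children with at least one dose, analysed as treated. AEs are to be summarised in it, but no measure is named.

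**The concern.** The aim and the AE definition cover all adverse events. The objectives and the one measure that counts children do not. A reader who wants the proportion of children on each arm with any adverse event will not find it among the stated outcomes, and the event total cannot supply it.

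Attribution is hard in this population. Section 7.1.6 lists nausea as a known effect of the device. The Rome IV footnotes to 4.2 list it as a supportive feature of postprandial distress syndrome and as one of the associated symptoms of abdominal migraine. The same episode can reasonably be put down to the device or to the disease, and for a non-serious event nobody beyond the site team reviews that call.

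What is at stake is how the safety comparison reads in a paediatric trial run for CE marking. The headline percentage would depend on causality judgements as well as on what happened to the children.

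**Working it through.** The Protocol states no AE rate and no AE sample size, so there is no figure of its own to reproduce. The check has three steps.

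**1. The two measures side by side.**

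| Measure in outcome 12 | Counts children? | Free of a relatedness judgement? |
|---|---|---|
| Percentage, possibly related | yes | no, for AEs; unclear for SAEs |
| Total number | no | yes |

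No stated measure has both properties. The total cannot be converted: 30 events may be 30 children with one event each or 10 children with three.

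**2. Does the filter change the comparison when both arms use the same attribution rule?** Inputs, all assumed: *b* = risk of a background AE, *c* = independent risk of a device-caused AE, *s* = share of caused events judged related, *f* = share of background events judged related.

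- All-cause risk difference = [1 − (1 − b)(1 − c)] − b = c(1 − b)
- Related-only risk difference = [1 − (1 − bf)(1 − cs)] − bf = cs(1 − bf)

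With b = 0.30 and c = 0.15, the all-cause figures are 40.5% v 30.0%, a difference of 0.15 × 0.70 = 10.5 points. Related-only, on the same events:

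| s | f | Related, Enterosgel v placebo | Difference | Against 10.5 |
|---|---|---|---|---|
| 1 | 0 | 15.0% v 0.0% | 15.0 | larger |
| 0.7 | 0 | 10.5% v 0.0% | 10.5 | equal |
| 0.5 | 0.2 | 13.05% v 6.0% | 7.05 | smaller |

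Over b = 0.20 to 0.40 and c = 0.05 or 0.15, the all-cause difference runs from 3.0 to 12.0 points. Related-only runs from 5.0 to 15.0 with perfect attribution (s = 1, f = 0) and from 2.3 to 7.2 with s = 0.5, f = 0.2. The related-only difference is the larger one when s(1 − bf) > 1 − b. The larger value is not an error: with perfect attribution it equals *c*, the caused risk itself. The point is that the result moves with *s* and *f*, which the trial does not measure.

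**3. The same in whole children.** Take 77 per arm (8.1), all dosed, and assume nausea AEs in 3 background cases per arm plus 6 caused cases on Enterosgel. Newcombe 95% CIs:

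- All-cause: 9 v 3, difference 6/77 = 7.8 points (−1.0 to 17.2).
- Related-only, half of the caused and 1 of 3 background cases kept per arm: 4 v 1, difference 3/77 = 3.9 points (−2.6 to 11.4).
- Related-only, all caused and 1 of 3 background cases kept per arm: 7 v 1, difference 6/77 = 7.8 points (0.5 to 16.4).

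One set of recorded events thus gives 3.9 or 7.8 points under equal attribution in the two arms.

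**The case against.** **This belongs in the SAP.** Section 8.2 leaves analysis detail to a SAP that is not shown, and tables of children with any AE are routine there. That stands in part: a SAP may well add them. But the Protocol is not silent. It names the child-level measure and words two objectives around it, and those would remain the filtered ones.

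**The wording may filter less than it seems.** It can be read as all SAEs plus related AEs. This stands. On that reading only non-serious AEs are filtered, and the ambiguity itself needs resolving. The Chief Investigator's review of SAE causality, the reporting of all SAEs to the MHRA and the Data Monitoring Committee are further safeguards, but none is described as a causality review of non-serious AEs.

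**Attribution-free information exists.** The PedsQL nausea and vomiting and constipation components (Table 1, outcome 5) are compared by arm, and the diary records doses missed through constipation or feeling unwell. This stands and lowers the importance. These are symptom scores and reasons for missed doses, not the share of children with an adverse event.

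**The related-only measure can be the sharper one.** In the 7 v 1 case its interval excludes zero and the all-cause interval does not. This stands, and is the reason to keep it as a supporting summary.

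Two stronger readings are tempting, and the documents support neither:

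- *That the filter hides harm.* Site attribution is blinded in weeks 3-6, so no direction can be presumed. Scenarios with a larger distortion (9 v 1, 10.4 points) need attribution to differ by arm despite blinding, and nothing in the Protocol suggests that it will.
- *That the placebo-to-open-label comparison must use the filtered percentage.* Objective 4 is "to compare the study outcome measures (same as for double-blind phase above) over the open-label" Enterosgel period, which could be taken to include outcome 12. But open-label safety has its own objective 6, which states no comparison, so objective 4 may well concern efficacy and quality of life only. If AEs were compared this way, knowing the treatment could move the result by itself. Suppose 77 placebo-first children have 3 background cases in each phase and no device effect, with 1 of 3 called related when blinded and 3 of 3 when open. The related percentage then goes from 1/77 = 1.3% to 3/77 = 3.9%, while the all-cause figure stays at 3.9%.

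**Conclusion.** The point holds as a weakness in how the safety outcome and objectives are defined. The only child-level AE measure depends on judged relatedness, made by the site alone for non-serious events, and the only all-cause measure cannot give the proportion of children affected. The related-only difference can be larger than, equal to or smaller than the all-cause one even with identical blinded attribution in both arms.

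Its size in this trial cannot be stated, because no AE rates are given; every rate and count above is an assumption chosen to show the mechanism. Importance is low to moderate. A reader might infer that all-cause safety data are lost; they are not, since 7.2.1 records every AE with its relationship and the all-cause percentage can be derived. The primary analysis is unaffected.

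**What to change.** 1. **Outcome 12.** Make the child-level measure the number and percentage of children in the safety population with at least one AE, and with at least one SAE, regardless of relationship. Report it by arm for the double-blind phase with risk difference and 95% CI, and descriptively by initial arm for the open-label phase.
2. **Supporting summaries.** Keep the possibly-related percentage and the event totals, and say whether the relatedness filter applies to SAEs.
3. **Objectives 3 and 6 (2.2.2 and Trial Summary).** Reword to: *reported adverse events, regardless of relationship, and separately those potentially related to treatment*.
4. **Placebo versus open-label period.** If AEs are compared across these periods at all, use the all-cause percentage, and note that open-label reporting may still differ.

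Cost: wording in three places and a few tables. No new data, no change in conduct and no effect on the primary analysis. The downside is a higher headline AE percentage and more background events in the all-cause comparison.

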3.3 DEFINITION OF END OF TRIAL

End of trial is defined as the last follow-up appointment for the last patient. Patients with unresolved SAEs at the last follow-up appointment would be followed up until SAE resolution or stabilisation.

4. STUDY PARTICIPANTS

4.1 INCLUSION CRITERIA

- 1) Written informed consent
- Children aged 3-18 years (parent/carer available to provide proxy-report and/or parent/carer report) with a clinical diagnosis of FAPD (Group H2a, H2b, H2c, H2d) according to the Rome IV criteria*
- 3) Normal faecal calprotectin at diagnosis (<250ug/g stool age 3-8 yrs, <100ug/g stool age 9-18 yrs)
- 4) Considered suitable to take part in the study by the consenting investigator
- 5) Diary completed on at least 11 of 14 days (≥75%) during the observational period
- 6) Able to complete questionnaires in English
- 7) Able to complete e diary and questionnaires on-line

4.2 EXCLUSION CRITERIA

- 1) Previously diagnosed coeliac disease, inflammatory bowel disease or other significant gastrointestinal disorder
- 2) Average number of stools per week <3
- 3) Previous use of Enterosgel®
- 4) Use of antidepressant agents, unless used at a stable dose for at least 6 weeks
- 5) Use of any probiotic supplements, other intestinal adsorbents, slow-release medications or strong

opioids

- 6) Participation in any research where treatment is provided in the last three months
- 7) Pregnancy or not willing to use contraception for the duration of the study**

* According to the Rome IV criteria for FAPD [H2; 21], the following criteria must be met for the last 3 months:

H2a. *Functional Dyspepsia*. Must include one or more of the following bothersome symptoms at least 4 times a month for at least 2 months prior to diagnosis:

- 1. Postprandial fullness
- 2. Early satiation
- 3. Epigastric pain or burning not associated with defecation
- 4. After appropriate evaluation, the symptoms cannot be fully explained by another medical condition

Within FD the following subtypes are now adopted:

H2a1. **Postprandial distress syndrome** includes bothersome postprandial fullness or early satiation which prevents finishing a regular meal. Supportive features include upper abdominal bloating, postprandial nausea, or excessive belching.

H2a2. **Epigastric pain syndrome** which includes all of the following: bothersome (severe enough to interfere with normal activities) pain or burning localized to the epigastrium. The pain is not generalized or localized to other abdominal or chest regions and is not relieved by defecation or passage of flatus. Supportive criteria can include (a) burning quality of the pain but without a retrosternal component, (b) commonly induced or relieved by ingestion of a meal but may occur while fasting.

H2b. Irritable Bowel Syndrome. Diagnostic criteria* Must include all of the following:

- 1. Abdominal pain at least 4 days per month over at least 2 months associated with one or more of the following:
- 2. Related to defecation and/or a change in frequency of stool and/or a change in form (appearance) of stool
- 3. In children with abdominal pain and constipation, the pain does not resolve with resolution of the constipation (children in whom the pain resolves have functional constipation, not IBS)

4. After appropriate evaluation, the symptoms cannot be fully explained by another medical condition *Criteria fulfilled for at least 2 months prior to diagnosis

Within IBS the following are subtypes:

- Abdominal pain associated with constipation (IBS-C)
- Abdominal pain associated with diarrhoea (IBS-D)
- Abdominal pain associated with constipation and diarrhoea mixed (IBS-M)
- Abdominal pain not otherwise specified (IBS-U)

H2c. Abdominal Migraine. Diagnostic criteria* Must include all of the following occurring at least twice:

- 1. Paroxysmal episodes of intense, acute periumbilical, midline or diffuse abdominal pain lasting 1 hour or more (should be the most severe and distressing symptom)
- 2. Episodes are separated by weeks to months
- 3. The pain is incapacitating and interferes with normal activities
- 4. Stereotypical pattern and symptoms in the individual patient
- 5. The pain is associated with two or more of the following:
 - a) Anorexia
 - b) Nausea
 - c) Vomiting
 - d) Headache
 - e) Photophobia
 - f) Pallor

6. After appropriate evaluation, the symptoms cannot be fully explained by another medical condition *Criteria fulfilled for at least 6 months prior to diagnosis

H2d. **Functional Abdominal Pain** – **Not Otherwise Specified** Diagnostic criteria* Must be fulfilled at least 4 times per month and include all of the following:

- 1. Episodic or continuous abdominal pain that does not occur solely during physiologic events (e.g., eating, menses)
- 2. Insufficient criteria for irritable bowel syndrome, functional dyspepsia, or abdominal migraine
- 3. After appropriate evaluation, the abdominal pain cannot be fully explained by another medical condition

*Criteria fulfilled for at least 2 months prior to diagnosis

^{**} A pregnancy test will be performed at Baseline on all female patients of child-bearing potential. Females of childbearing potential (over the age of 11 years; not surgically sterile (hysterectomy or bilateral oophorectomy), 12 months postmenopausal or otherwise incapable of pregnancy) and heterosexually active must use contraception throughout the screening period and the 8 weeks when they may be receiving study treatment. Acceptable methods of contraception are methods that can achieve a failure rate of less than 1% per year when used consistently and correctly are considered as highly effective birth control methods. Such methods include [23]:

- combined (oestrogen and progestogen containing) hormonal contraception associated with inhibition of ovulation:
 - o oral
 - o intravaginal
 - o **transdermal**
- progestogen-only hormonal contraception associated with inhibition of ovulation:
 - o oral
 - o *injectable*
 - o implantable
- *intrauterine device (IUD)*
- intrauterine hormone-releasing system (IUS)
- bilateral tubal occlusion
- vasectomised partner (Vasectomised partner is a highly effective birth control method provided that partner is the sole sexual partner of the woman of childbearing potential trial participant and that the vasectomised partner has received medical assessment of the surgical success)
- sexual abstinence (In the context of this guidance sexual abstinence is considered a highly effective method only if defined as refraining from heterosexual intercourse during the entire period of risk associated with the study treatments. The reliability of sexual abstinence needs to be evaluated in relation to the duration of the clinical trial and the preferred and usual lifestyle of the subject.)

Method of contraception must be documented in the patient's medical records.

